8.1.1. Study medication

This study is designed as a phase Ib 8 week monocentric, randomized, double-masked, vehicle controlled, parallel groups study (referred to as the controlled treatment period) followed by a 24 week follow-up period (4 weeks masked follow-up and additional 20 weeks unmasked follow-up).

The 60 consecutively enrolled patients will be randomized in a 2:1 ratio to the active treatment arm (rhNGF 180 µg/ml, one drop TID) or to the vehicle arm (vehicle, one drop TID) during the 8 week treatment period.

On the Day 0 Visit the first 2 doses (1 dose = 1 drop) of study medication will be administered in the clinic by study site personnel and the patient will be monitored for adverse events. In the absence of any clinically significant side effects in the opinion of the investigator the patient will be dispensed their study medication and instructed to self-administer the 3rd dose of Day 0 at home 6 hours after the 2nd dose of study medication was given. The patient will also be instructed to return to the study clinic after 1 week for Week 1 Visit.

Patients enrolled in the study will continue their 8 week treatment and will later enter the 24 week follow-up period without interruption.

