9. INVESTIGATIONAL PRODUCT

9.1. IDENTITY OF STUDY TREATMENT

The Test product is a form of recombinant human Nerve Growth Factor (rhNGF) produced in *E.coli* developed by Dompé R&D Laboratories. rhNGF is a sterile 0.18 mg/mL single use lyophilized preparation, packaged in a glass vial, and administered after reconstitution with 0.3 ml of sterile WFI contained into a glass prefilled syringe. The WFI prefilled syringe is used with an adaptor consisting of a connecting device with dual connections: one end for the glass-syringe and one end for the vial. The drug product will be manufactured under environmental and process aseptic conditions in accordance with GMP guidelines to obtain a final sterile drug product.

Test product: Recombinant human nerve growth factor 180µg/ml (one 35 µl drop equals to 6.30 µg of rhNGF) reconstituted solution

Vehicle Control: Ophthalmic Placebo solution of the same composition as the test product with the exception of rhNGF reconstituted solution

Investigational product will be provided as a 4-weeks kit formed by two boxes: the first box containing the vials (lyophilized product) and the second box containing adaptors and prefilled 0.3 ml WFI syringes. Each vial after reconstitution contains a volume of 0.3 ml rhNGF 180 µg/ml or control. A training manual for investigators with detailed instructions on how to reconstitute the eye drops from the lyophilized product is provided in Appendix A.

The clinical labeling of the investigational product will be done in a manner that protects the masking of the study medication. It will include a statement of caution and describe particulars applicable to regulatory requirements (e.g.: kit number, protocol number, storage conditions, name and address of the sponsor, statement that the product is for investigational use only, etc.).

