**9.1.5. Storage**

Investigational product must be stored in a secure area at the investigational site as per the labeling instructions. A temperature probe and data logger will accompany the drug on shipment. It is essential that the Investigational sites verify the temperature range reached during shipment, so that potential stability concerns during shipment can be discovered and appropriate action taken. The box of the investigational product containing the lyophilized preparation must be stored at 2-8°C at the Investigational sites (preferably at the pharmacy of the hospital), whereas the box containing the prefilled syringes and adaptors may be kept at room temperature. Eligible patients will receive the first 4-week kit of study medications in a refrigerated bag containing the investigational product. The vehicle control will be also dispensed in a refrigerated bag. The patient will be instructed to store the study medication (the box of the investigational product containing the lyophilized preparation) at home in the refrigerator at 2-8 °C for the entire 4 weeks until next visit. The box containing the prefilled syringes and adaptors may be kept at room temperature. When the patients will start to use the study medications at home each day they will remove from the refrigerator only the vials to be used over the course of the day. Patients will use one vial to instill one drop in both eyes three times per day.

A daily temperature log will be maintained at the site for documenting appropriate storage conditions and will be made available for the study monitor to inspect. Any deviations from the recommended storage conditions should be immediately reported to Dompé and the use of the drug suspended until authorization for its continued use has been given by Dompé.

Investigational products will be supplied as a lyophilized preparation in glass vials together with a prefilled 0.3 ml sterile WFI syringes and adaptors. The vials will be labeled with the appropriate clinical study labeling. The vehicle of rhNGF will be supplied in glass vials identical to those containing rhNGF with a prefilled 0.3 ml WFI syringes and adaptors. The vials containing the vehicle will be labeled with the appropriate clinical study labeling. Investigational product will be kept in an identical box to ensure double-masking.

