7.2.5 Measurements of Exposure and Treatment Compliance

The patients will be dispensed a 4 week supply of study medication (1 kit) on the Day 0 visit and at Weeks 4.

Patients will also be instructed to bring back to the clinic at each study visit all the used and unused vials.

Each 4 week kit will be composed of 1 box containing a total of 90 single-use vials of the randomized / assigned medication for daily treatment during 4 weeks and 1 box containing the same number of adaptors and prefilled 0.3 ml WFI syringe.

[figure not shown]
All patients will be dosed one drop (35 µl) three times a day (TID) in each eye during the 8 weeks treatment period.

Exposure

Information on Exposure will be derived from information on eCRF Pages 'Study Drug Dosing Dates' (Date of First Study Drug Administration, Date of Last Study Drug Administration), 'End of Study' (Date of Study Discontinuation/Completion), 'Study Visits' (Date of Week 8) as well as 'Study Drug Dosing and Accountability' (Date of Vial Dispensed/Returned, Days without Treatment).

Exposure will be presented by displaying Duration of Treatment Period, Duration of Follow-up Period, Extent of Exposure and Days on Study Medication, which will be derived as follows

- Duration of Treatment Period:
Week 8 Visit Date or Date of Study Discontinuation/Completion – Date of First Study Drug Administration + 1, whatever is earlier.
- Duration of Follow-Up Period:
Date of Study Discontinuation/Completion – Date of Week 8, for all patients who have completed the treatment period and terminated the study (regularly or prematurely)
For patients who did not complete the treatment period, Duration of Follow-Up Period is set to 0.
Main Objectives Analysis only: if a patient has not completed the study yet, the last documented visit during Follow-Up Period (including unscheduled visits) will be considered for calculating Duration of Follow-Up Period.
- Extent of Exposure (days) = (Date of Last Study Treatment – Date of First Study Treatment Administration + 1),

If Date of Last Study Treatment is missing (e.g. due to Lost to Follow-Up), Date of Study Discontinuation/Completion or Date of Last Study Drug Return (as documented on the eCRF Page ‘Study Drug Dosing and Accountability’) will be used, whatever is earlier.

- Days on Study Medication = Sum of (Date of Vial Returned – Date of Vial Dispensation – Days without Treatment) +1 for all lines in eCRF Page ‘Study Drug Dosing and Accountability’.

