If no Vials are dispensed, Days on Study Medication will be set to 0. In case of incomplete/inconsistent documentation on eCRF, Days on Study Medication will be set to Missing.

Compliance

Patient compliance with the study medication will be assessed at each study visit following the dispensing of the study medication for self-administration. For each kit dispensed, the eCRF page ‘Study Drug Dosing and Accountability’ records per return visit:

- Date dispensed
- Kit number received
- Number of vials dispensed
- Date returned
- Number of vials returned
- Number of vials unused
- Number of days without treatment

Compliance will be evaluated according to the following formula:

$$\text{Compliance (\%)} = 100 * \frac{\text{Number of vials dispensed} - \text{Number of unused vials returned}}{\text{Number of expected days on treatment}}$$

The number of expected days on treatment will be set to 56. For each patient, the number of vials dispensed will be derived as the sum of provided numbers in the column “# Vials Dispensed” on the eCRF Page ‘Study Drug Dosing and Accountability; the number of unused vials returned will be derived as the sum of provided numbers in the column “# Vials Unused” on the eCRF Page ‘Study Drug Dosing and Accountability’.

Compliance will be presented categorical as <80%, ≥80%.

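### The compliance formula divides vials by 56 days with no vials-per-day factor: at the three vials a day the kit implies, full use scores 300% and 45 of 168 vials (27%) counts as at least 80%

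*SAP*

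**What the plan says.** SAP 7.2.5 defines compliance as 100 times a ratio. The numerator is the total vials dispensed less the total unused vials returned, both summed from the drug accountability eCRF page. The denominator is a number of days, the same for every patient: "The number of expected days on treatment will be set to 56". The result is shown only in two classes: "Compliance will be presented categorical as <80%, ≥80"%. SAP 10.5 sends it to Table 14.1-7.2 for the ITT and lists the underlying data.

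The same SAP section describes the supply: "Each 4 week kit will be composed of 1 box containing a total of 90 single-use vials", with one kit given at Day 0 and one at Week 4, and dosing of one drop TID in each eye for 8 weeks. Protocol 9.1.2 gives the same kit contents, and Protocol 9.1 also calls the product single use.

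On daily handling, Protocol 9.1.5 says that patients at home take out vials in the plural: "they will remove from the refrigerator only the vials to be used over the course of the day". It then adds: "Patients will use one vial to instill one drop in both eyes three times per day". On volume, Protocol 9.1 says: "Each vial after reconstitution contains a volume of 0.3 ml".

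**The concern.** The numerator is in vials and the denominator in days. Their ratio is a percentage of expected use only if the plan is one vial per day, and the SAP never says that. If the plan is three, every score is three times too large and the 80% cut falls far below 80% of planned use.

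The primary objective is the safety and tolerability of a TID regimen, so readers will use compliance to judge whether patients received that regimen. Extent of Exposure and Days on Study Medication count whole days. The eCRF item that feeds the latter, "Number of days without treatment", is also in whole days. Doses missed within a day can therefore show only in the vial-based table. Because that table is dichotomised, a score of 300% would never appear in it.

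**Working it through.** **Inputs**
- Denominator 56 and cut 80%: SAP 7.2.5.
- 90 single-use vials per 4-week kit, two kits per patient, TID dosing in each eye, 35 µl per drop: SAP 7.2.5 and Protocol 9.1.2.
- Vial volume 0.3 ml: Protocol 9.1.
- Vials per day: not stated unambiguously, so both readings are worked.

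**The plan's own figure.** 8 weeks × 7 = 56 days. The denominator reproduces, but as days.

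**Vials per day implied by the kit.** 90/28 = 3.2 per day. At three a day a kit needs 28 × 3 = 84 vials, leaving 6 spare.

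**Reading A: three vials per day**
- Planned use: 3 × 56 = 168 vials.
- Score at full use: 100 × 168/56 = 300%.
- Score at 80% of planned use: 100 × 0.8 × 168/56 = 240%.
- Smallest count classed as at least 80%: 0.8 × 56 = 44.8, so 45 vials (44/56 = 78.6%; 45/56 = 80.4%).
- As a share of planned use: 45/168 = 26.8%, or 45/3 = 15 of 56 days of full dosing.
- Cut with 168 as denominator: 0.8 × 168 = 134.4, so 135 vials (134/168 = 79.8%; 135/168 = 80.4%).
- Wrong category: everyone using 45 to 134 vials (26.8% to 79.8% of planned use).

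| Vials used | SAP score (÷56) | Share of planned vials (÷168) |
|---|---|---|
| 45 | 80.4% | 26.8% |
| 56 (one a day) | 100% | 33.3% |
| 112 (two a day) | 200% | 66.7% |
| 168 (three a day) | 300% | 100% |
| 180 (none returned unused) | 321% | 107.1% |

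**Reading B: one vial per day**
- Volume: 6 drops × 35 µl = 210 µl, which fits in 300 µl.
- Planned use: 56 vials. Full use scores 56/56 = 100%, and 45 vials is 80.4% of expected use, so the formula works.
- But each kit would leave 90 − 28 = 62 vials unused. The first kit alone would cover all 56 days with 90 − 56 = 34 left over, so the second kit would not be needed. A vial opened three times a day is also not single use.

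**Does a fixed 168 tolerate the Week 8 window?** Full dosing for 49 days, the earliest visit in the window, gives 3 × 49 = 147 vials, and 147/168 = 87.5%, still above the cut. Two kits cap the score at 180/168 = 107.1%.

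**Day 0 clinic doses.** Protocol 8.1.1 says "the first 2 doses (1 dose = 1 drop) of study medication will be administered in the clinic". If these do not come from the patient's kit, expected kit use on reading A is 168 − 2 = 166, and the cut is 0.8 × 166 = 132.8, so 133 vials.

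**The case against.** The strongest objection is that every figure above 100% depends on three vials per day. The sentence in Protocol 9.1.5 that ties vial use to the dosing frequency can be read as one vial for the whole day. The volume allows it, and 56 would then be the right denominator. This stands as an ambiguity, and the sentence can equally mean one vial per instillation. It does not rescue the plan: the one-vial reading contradicts the single-use label, the 90-vial kit and the plural daily vials in Protocol 9.1.5 (also in 9.1.3 and 10.2.2).

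Four further points have some force.
- The shares are of planned vials, not of doses taken. Since one vial could physically supply six drops, a patient using one a day may have instilled every dose by reusing vials. This is accepted, and the table above is labelled accordingly.
- A patient who stopped after 15 days would show an Extent of Exposure of 15 days in Table 14.1-7.1. So the extreme case is partly visible elsewhere; doses missed within a day are not.
- Scores near 300% in Listing 16.2.5-1.1 might be caught by the sensibility review in SAP 5.3. That makes the error detectable but does not correct the specification, and double programming would reproduce it.
- A fixed 168 scores a fully adherent patient who exits at Week 4 as 84/168 = 50%. This is true, but any fixed denominator has this property, including the SAP's own 56 on the one-vial reading (28/56 = 50%).

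**Conclusion.** The point holds: the compliance rule and the vial description cannot both be right as written. On the three-vial reading, which the kit size, the single-use label and the second kit support, the formula is too large by a factor of 3. Full use scores 300%, the 80% cut sits at 26.8% of planned use, and patients using 45 to 134 vials are shown as at least 80% when they belong below. The vial text, not the formula, needs correcting only if one vial a day is confirmed.

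That the units do not match and the passages are unreconciled is certain; the 300% and 27% figures rest on three vials per day. The consequence is limited to Table 14.1-7.2, the compliance value in Listing 16.2.5-1.1, and how they are read. Compliance defines no analysis set (SAP 6.1) and enters no primary outcome (7.2.7, 7.2.8) or test (8.2, 8.3), and the raw vial counts are listed. It should be fixed, but it does not threaten the main results.

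**What to change.** 1. The sponsor should reconcile Protocol 9.1.5 with the kit description in Protocol 9.1.2 and SAP 7.2.5, and state the planned number of vials per day in the SAP.
2. Replace the denominator with expected vials = planned vials per day × 56. This is 168 on the reading the kit supports. It stays 56 only if one vial a day is confirmed, and then the single-use and 90-vial text must be corrected.
3. Keep the 80% cut. With 168 it falls at 135 vials.
4. State whether the two Day 0 clinic doses come from the patient's kit. If they do not, then on the three-vial reading expected kit use is 166 and the cut is 133 vials.
5. Optionally, show the number of vials not returned, which the formula counts as used.

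The cost is one line in the SAP and one ADaM derivation. No new data are needed, because vials dispensed and vials unused are already on the eCRF.

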8.1.2. Other medications

Upon enrolment, the previous topical glaucoma medications of patients will be continued normally, however, it will be required that previous topical ophthalmic medications used for intraocular pressure control will not be changed during the course of the study. Any other topical ocular treatment not related to intraocular pressure control for glaucoma, that is used before enrollment, will need to be discontinued and patients will only be allowed to use the study medication provided by Dompé and preservative-free artificial tears during the course of randomized controlled treatment period.

No rescue medication is planned for this study.

8.2. 24 WEEK FOLLOW-UP PERIOD

At the conclusion of the controlled treatment period at Week 8, patients will be discontinued from study treatment. During the 24 week follow-up period (Weeks 9-32) the patients will be followed without any protocol required study medication, however, preservative-free artificial tears (not provided by Dompé) may be prescribed as needed as at the discretion of the study investigator.

The first 4 weeks of the follow up period will be referred to as masked follow-up (and patients treatment will be kept masked) while the following 20 weeks will be referred to as unmasked follow-up (patients treatment will be unmasked at week 12) and the database will be locked. The database will be locked and the study will be complete after the last randomized patient has completed 4 weeks of the follow up period (Week 12 Visit). However, after the database lock patients still in the follow up period will continue with scheduled visits for the remainder of the 24 week follow up period.

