Table 2: Study Visits

Scheduled Visit	Scheduled Visit Label	Scheduled Study Day	Visit Window
Screening Visit	Screening	Before Baseline Visit	Up to 4 weeks before date of Baseline Visit
Baseline Visit Day 0	Baseline	0	Date of Baseline Visit – Date of First Study Treatment in [-1, 0]
Week 1	Week 1	7	Visit date – Date of First Study Treatment in [5 – 9]
Week 4	Week 4	28	Visit date – Date of First Study Treatment in [24 – 32]
Week 8	Week 8	56	Visit date – Date of First Study Treatment in [49 – 63]
Follow-up Visit Week 12	Week 12	84	Visit date – Date of First Study Treatment in [77 – 91]
Follow-up Visit Week 32	Week 32	224	Visit date – Date of First Study Treatment in [217 – 231]
Documented unscheduled Visits will be labeled as “Unscheduled Visit x.01”, “Unscheduled Visit x.02”, “Unscheduled Visit y.01”... .			
Date of First Study Treatment is to be taken from eCRF page “Study Drug Dosing Dates”.			

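### Compliance divides vials used by a fixed 56 days: the unit is off by a factor of about three, and each patient's actual treatment length is ignored

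*SAP*

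**What the plan says.** Under Compliance in SAP 7.2.5, the numerator is a vial count taken from the accountability page: "the number of vials dispensed will be derived as the sum of provided numbers", and from this is subtracted a second total, since "the number of unused vials returned will be derived as the sum of provided numbers". The denominator is a day count, the same for everyone: "The number of expected days on treatment will be set to 56". The percentage is then cut into two classes: "Compliance will be presented categorical as <80%, ≥80" per cent. SAP 10.5 summarises these classes by treatment group for the ITT (Table 14.1-7.2).

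Four other statements bear on that denominator:

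- **Supply.** Protocol 9.1.2 and SAP 7.2.5 give each patient two 4-week kits (Day 0 and Week 4), each of 90 single-use vials, for dosing three times a day.
- **Visit window.** Table 2 in SAP 7.1 accepts a Week 8 visit with "Visit date – Date of First Study Treatment in [49 – 63" days.
- **End of dosing.** Protocol 8.2 says "At the conclusion of the controlled treatment period at Week 8, patients will be discontinued from study treatment".
- **Actual duration.** Under Exposure, SAP 7.2.5 derives a Duration of Treatment Period for each patient from "Week 8 Visit Date or Date of Study Discontinuation/Completion", taking the earlier date, minus the first-dose date, plus one day.

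**The concern.** A compliance percentage is readable only if numerator and denominator share a unit and cover the same period. Here neither condition is met. The numerator grows by the number of vials used per day and by the number of days the patient is actually on treatment. The denominator reflects neither.

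The trial's primary objective is safety and tolerability, so readers will want to know whether patients took the drug. Table 14.1-7.2 is the only vial-count summary and the only one with a compliance threshold. If the ≥80% class admits patients who used a quarter of their drops, it says almost nothing. If only the unit is repaired, visit timing and early exit are counted as adherence, and an arm with more early exits would look less adherent even if every patient took every dose while in the study.

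**Working it through.** **The plan's own figure.** 8 weeks × 7 days = 56 days. The number is right as a count of planned days.

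**Inputs.**
- Cut-off: 80% (SAP 7.2.5).
- Week 8 window: 49 to 63 days after first dose (SAP 7.1, Table 2).
- Supply: 2 kits × 90 = 180 vials (SAP 7.2.5).
- Vials per day: taken as 3. This is an inference. Three single-use vials a day for 28 days is 84, which fits a 90-vial kit with 6 spare. The sentence on vial use in Protocol 9.1.5 could, read alone, mean one vial a day, so that case is shown as well.

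**Formulas.**
- Score as written, full adherence = 3 × days / 56.
- Vials needed for the ≥80% class as written = 0.80 × 56 = 44.8.
- With the unit corrected, the denominator is 56 × 3 = 168 vials and the cut-off is 0.80 × 168 = 134.4 vials.
- True adherence at the cut-off = cut-off vials / (3 × days).

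| Days of dosing | Expected vials | Full-adherence score, as written | True adherence at cut-off, as written | Full-adherence score, base 168 | True adherence at cut-off, base 168 |
|---|---|---|---|---|---|
| 49 | 147 | 262.5% | 30.5% | 87.5% | 91.4% |
| 56 | 168 | 300% | 26.7% | 100% | 80.0% |
| 63 | 189 | at most 321.4% | 23.7% | at most 107.1% | 71.1% |

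The day-63 scores are limited by supply: 180/56 = 321.4% and 180/168 = 107.1%. Without that limit they would be 337.5% and 112.5%.

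**Time to reach the cut-off as written.** 44.8 / 3 = 14.9, so about 15 days of full dosing.

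**Early exit with full adherence.**
- Day 20: 60/56 = 107% as written; 60/168 = 35.7% on base 168.
- Day 40: 120/56 = 214% as written; 120/168 = 71.4% on base 168.
- Both patients are classed ≥80% now, and both would be classed <80% if only the unit were repaired.

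**Counting the extra day.** The SAP's duration adds one day, so the window becomes 50 to 64 days. As written, true adherence at the cut-off is 44.8/150 = 29.9% to 44.8/192 = 23.3%. On base 168 it is 134.4/150 = 89.6% to 134.4/192 = 70.0%.

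**If one vial a day were meant.** The unit error disappears, and the formula as written gives 44.8/49 = 91.4% to 44.8/63 = 71.1%. The window error is therefore the same at any constant number of vials per day: 49/56 is 12.5% low and 63/56 is 12.5% high, before the supply limit.

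**Repairing one part only.** Replacing 56 by actual days without the vial factor leaves full adherence at 3 × days / days = 300%. Using 168 without actual days leaves the last two columns of the table. Both changes are needed.

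**The case against.** The strongest reply is that little depends on this table. Compliance is a two-class descriptive summary. SAP 6.1 defines no per-protocol set and no analysis set that uses it, and no test uses it. Adverse event percentages are taken over patients (SAP 8.1). That stands, and it limits the weight of the point.

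A second reply is that a fixed 56 measures adherence to the planned course, which is a recognisable choice. It could justify a fixed 168 vials, but not 56 days under a vial count. Treatment length is already reported through Duration of Treatment Period and Extent of Exposure.

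A third is that the day-63 figures assume dosing continues to a late visit. The documents also speak of 8 weeks of treatment; a patient who stops at day 56 scores 168/168 on the unit-corrected base. That is fair for the upper edge. The day-49 and early-exit results do not depend on it.

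Three stronger readings are tempting, and the documents do not support them:

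- A reader might infer that the 80% cut-off, as now written, means 71% to 91% adherence. That needs one vial a day or a denominator already converted to vials. The kit size points to about three a day, which gives about 24% to 31%.
- A reader might infer that early leavers are now classed as non-compliant. At three vials a day this happens only for exits before about day 15.
- A reader might take Table 14.1-7.2 to be the only by-arm statement on dose-taking. SAP 10.5 also summarises Days on Study Medication by group, which subtracts recorded days without treatment and does not use 56.

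**Conclusion.** The point holds and should be corrected, though it is not critical. The larger defect is the unit: at about three vials a day, the ≥80% class accepts patients who used roughly a quarter to a third of their expected vials, so it hardly discriminates. The smaller defect is the fixed duration, worth up to 12.5% either way across the permitted window and more for early exits. It would become visible as soon as the unit alone was repaired.

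The size of the unit error rests on three vials a day, inferred from the kit contents and the dosing frequency. The size of the duration error does not depend on that, but its upper side assumes dosing up to a late Week 8 visit. The consequences stop at Table 14.1-7.2 and the compliance entries in Listing 16.2.5-1.1.

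**What to change.** In SAP 7.2.5, replace the fixed denominator with expected vials per day × the patient's own Duration of Treatment Period, and keep the 80% cut-off:

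Compliance (%) = 100 × (vials dispensed − unused vials returned) / (expected vials per day × Duration of Treatment Period).

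Three matters need settling alongside it:

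- Reconcile the vial-use sentence in Protocol 9.1.5 with the 90-vial kit, and state the resulting vials per day in the SAP.
- State whether the visit day counts as a dosing day, since the derived duration includes it.
- State how a Week 8 visit after day 56 is handled, because the documents describe both an 8-week course and an end of dosing at Week 8. If dosing runs to day 63, supply limits the score to 180/189 = 95.2%. If it stops at day 56 with a day-63 visit, full adherence scores 168/189 = 88.9%. Neither falls below the cut-off.

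The cost is one sentence and one changed variable, with no new data. The small loss is that compliance no longer refers to the full planned 8 weeks; Extent of Exposure and Duration of Treatment Period still show that.

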**Table 9.1.2-1 - Kit Assignments**

| Weekly visit | # of kits |
|---|------------------|
| Day 0 - Randomization / Therapy initiation Visit | 1 kit |
| Week 4 Visit | 1 kit |

Study medications that will be dispensed to the patient during the study visits will be distributed in refrigerated bags. In addition to the study medication to be administered in the clinic on the day of the study visit, patients will also be instructed to bring back to the clinic at each study visit all the used and unused vials by placing them in the refrigerated bag that was given at the Day 0 visit (so that it can be used for dispensing the next kit, if applicable).

Each 4 week kit will be composed of 1 box containing a total of 90 single-use vials of the randomized / assigned medication for daily treatment during 4 weeks and 1 box containing the same number of adaptors and prefilled 0.3 ml WFI syringe.

All patients will be dosed one drop (35 µl) three times a day (TID) in each eye during the 8 weeks, randomized, double-masked, controlled treatment period.

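### The SAP compliance formula has no rule for a kit that is never returned, so its vials count as used and the patient is classed as at least 80% compliant; the exposure fallback has a narrower gap

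*SAP*

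**What the plan says.** Supply: "The patients will be dispensed a 4 week supply of study medication (1 kit) on the Day 0 visit and at Weeks 4" (SAP 7.2.5). Protocol 9.1.2 gives the content: "Each 4 week kit will be composed of 1 box containing a total of 90 single-use vials".

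Compliance (SAP 7.2.5): 100 × (vials dispensed − unused vials returned) / expected days. On the denominator: "The number of expected days on treatment will be set to 56". On the quantity subtracted: "the number of unused vials returned will be derived as the sum of provided numbers in the column" for unused vials. The result is split at 80% with no upper limit and tabulated for the ITT (SAP 10.5). The same eCRF page also records the number of vials returned, but the formula does not use it.

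Extent of Exposure (SAP 7.2.5): last treatment date − first treatment date + 1. The fallback begins: "If Date of Last Study Treatment is missing (e.g. due to Lost to Follow-Up), Date of Study Discontinuation/Completion". The alternative is the date of the last drug return, and the earlier of the two applies.

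Days on Study Medication, in the same section, is treated differently: "In case of incomplete/inconsistent documentation on eCRF, Days on Study Medication will be set to Missing".

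**The concern.** The subtraction removes only vials that came back and were counted as unused. A vial that stays at the patient's home is never subtracted, so the formula treats it as taken. SAP 7.2 says that missing-value handling is specified for each variable where applicable, and SAP 8.4.2 says that nothing is imputed. For an unreturned kit, the compliance formula in effect imputes full use. A few lines earlier, the SAP accepts that an incomplete record leaves Days on Study Medication unknown.

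The primary objective is safety and tolerability, and readers use the compliance and exposure tables to judge how much drug lies behind that result. With 40 and 20 patients planned per arm, one misclassified patient moves the compliance percentage by 1/40 = 2.5 points (rhNGF) or 1/20 = 5 points (vehicle).

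The exposure fallback raises a related question: with no return date, only an administrative date is left to stand for the last dose.

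**Working it through.** **Inputs.** 90 vials per kit and kits at Day 0 and Week 4 (Protocol 9.1.2, SAP 7.2.5), so 180 vials in all. Denominator 56 (SAP 7.2.5), which reproduces as 8 weeks × 7 days.

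**Vials per day.** The documents are not clear. A kit of 90 single-use vials for 4 weeks fits one vial per dose (28 × 3 = 84, leaving 6 spare). The sentence on vial use in Protocol 9.1.5 can also be read as one vial for the day. Both readings are shown.

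**Compliance at three vials a day** (full use = 56 × 3 = 168 vials):

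| Patient (illustrative) | As written, /56 | On 168 vials | True use |
|---|---|---|---|
| Kit 1 returned with 6 unused; kit 2 collected, dosing stops that day, kit 2 never returned | (180 − 6)/56 = 310.7% | 174/168 = 103.6% | 84/168 = 50% |
| Lost with kit 1, nothing returned | 90/56 = 160.7% | 90/168 = 53.6% | e.g. last dose on day 10: 10/56 days = 17.9% |
| Both kits unreturned | 180/56 = 321.4% | 180/168 = 107.1% | unknown |

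As written, all three are classed ≥80%.

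**Separating two faults.** On this reading, a fully compliant patient who returns 12 unused vials scores 168/56 = 300%, because vials are divided by days. Much of the excess in the /56 column is that separate fault. The 168 column removes it: the first patient stays ≥80%, and the second drops below 80%.

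**Compliance at one vial a day** (full use = 56 vials, so 56 is the right denominator). Kit 1 returned with 90 − 28 = 62 unused and kit 2 never returned gives (180 − 62)/56 = 210.7%, against true use of 28/56 = 50%. Lost with kit 1 only gives 90/56 = 160.7%. Here the whole excess comes from unreturned vials.

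**Extent of Exposure, last-dose date missing.**

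- No kit ever returned: only the exit date is left. Assumed exits 28, 42, 63 and 84 days after first dose give 29, 43, 64 and 85 days. If true exposure is assumed to be 10 days, the excess is 19, 33, 54 and 75 days. No cap is stated, and SAP 7.2.1 allows for exits later than 63 days after first dose. The patient held one 4-week kit.
- Kit 1 returned 28 days after first dose, then lost with kit 2: the earlier date applies, giving 28 + 1 = 29 days. If dosing in fact ran for 35 to 56 days, the rule understates exposure by 6 to 27 days.

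**The case against.** Most patients who merely stop are covered. Protocol 10.5 and SAP 3.3 require early exits up to Week 8 to undergo the Week 8 procedures. Those include the compliance check, and the Study Plan has patients return used and unused product at Week 8. A recorded last-dose date bypasses the exposure fallback altogether. This stands: the affected group is mainly patients lost without returning a kit.

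Where nothing at all was returned, no unused count is provided, and the SAP does not say whether the sum is then zero or missing. That is fair for the patient holding only kit 1; the 160.7% assumes zero. It does not help where kit 1 was returned and kit 2 was not: the sum of the provided numbers is then 6 and the score is determinate.

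A reader might infer that drop-outs in general are credited with too much exposure. The documents do not support that. It takes a missing last-dose date, no kit ever returned and a late exit date together, and a patient who returned kit 1 may be credited with too little. The case of a patient lost after Week 1 further assumes that no return was logged at that visit. SAP 7.2.5 asks for vials back at each visit, while the schedule places the compliance check at Weeks 4 and 8.

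A reader might also infer that poor tolerability is hidden. It is not: the SAP tabulates TEAEs leading to treatment withdrawal and to study discontinuation, reasons for discontinuation by period, and the VAS scores. It also lists treatment interruptions and every patient's exposure and compliance data.

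**Conclusion.** The compliance point holds. As written, a patient with an unreturned kit is classed ≥80% whatever was taken. Correcting the denominator alone does not cure this when kit 1 came back and kit 2 did not (103.6% against 50%). For a patient lost with kit 1 only, it does change the class on the three-a-day reading (53.6%), though not on the one-a-day reading.

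The exposure point holds in a limited form: the fallback can overstate or understate, depending on whether any kit was returned.

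The reach is modest. Compliance is one descriptive ITT table and exposure one descriptive safety-set table. Neither defines an analysis set or enters a model, AE percentages use patient counts, and no exposure-adjusted AE rate is planned. The documents give no drop-out rate, so the number of patients affected cannot be estimated. The stopping days and exit dates used here are assumptions.

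**What to change.** Amend SAP 7.2.5:

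- **Compliance.** Do not count the vials of an unreturned kit as used. Add a not-evaluable category for patients with an unreturned kit, show the number of unreturned vials per arm, and give the range from none used to all used. At three vials a day, that range is 84/168 = 50% to 174/168 = 103.6% for the first patient above, and 0% to 53.6% for the second.
- **Exposure.** Where the last-dose date is missing, cap the fallback at the last attended study visit plus the supply then in hand. It should never run past the end of supply of the last kit dispensed or the end of the treatment period. Flag the value as imputed. Taking a kit as its nominal 4 weeks, the 85-day example falls to at most 28 days. The cap does not lengthen the 29-day case; the flag warns the reader that it may be short.
- **Vials per day.** Reconcile Protocol 9.1.2 and 9.1.5, and put numerator and denominator in the same unit.

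Vials returned minus vials returned unused should not become the sole numerator. It would score discarded empty vials as missed doses, and the SAP does not say whether the returned count includes unused vials.

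The cost is SAP wording and programming, using vial counts, dispensing and return dates and visit dates already collected. The small downside is that some patients become not evaluable.
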